10.11. Appendix 11: Staff Study Participant Survey

A survey will be administered to the staff study participants at three timepoints:

- Month 1 – following the investigator meeting, but prior to any patients at the site receiving the CAB+RPV injection
- After the 4th monthly facilitation call
- Month 12/ End of Study

The first two surveys will include approximately 55 questions and will take about 15 minutes to complete. The final survey will include approximately 100 questions and will take about 25 minutes to complete. Staff study participants will be asked to answer the questions at Month 1 based on their current expectations of administering the CAB+RPV injection, and at the following timepoints based on their current experience administering the injection.

The following concepts are measured in the staff study participant surveys:

- Acceptability of the CAB+RPV injection (AIM)
- Appropriateness of the CAB+RPV injection (IAM)
- Feasibility of the CAB+RPV injection (FIM)
- Facilitators and barriers to implementation of the CAB+RPV injection
- Utility of toolkit and study resources
- Experiences and attitudes about the CAB+RPV injection
- Sustainability of the CAB+RPV injection (PSAT) (Month 12 only)

Acceptability, appropriateness and feasibility will be measured by the Acceptability of Intervention Measure (AIM), the Intervention Appropriateness Measure (IAM) and the Feasibility Appropriateness Measure (FIM), which are constructs validated from the Proctor Framework. Responses are measured using a 5-point Likert scale. ([Weiner, 2017](#))

Additional questions are included to evaluate facilitators and barriers from the site perspective. A series of questions are also included to evaluate the usefulness of toolkit resources, and about staff study participant experiences and attitudes towards implementing the CAB+RPV injection.

Sustainability is measured by the Program Sustainability Assessment Tool (PSAT). The PSAT evaluates the capability of clinics to maintain processes developed to administer CAB+RPV injection in routine clinical settings after the conclusion of this study. ([Luke, 2014](#))

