Month 1, prior to receiving injection	Survey (100% of patient study participants)	Baseline: (prior to first subject Month 1 visit at the site)	Survey of lead HIV provider	Survey of nurse/person delivering CAB + RPV LA injections	Survey of clinic administrator/ manager
After Baseline, Prior to First Injection	Semi-structured Interviews (up to 4 patient study participants per site)		Semi-structured Interviews of lead HIV provider	Semi-structured Interviews of nurse/person delivering CAB + RPV LA injections	Semi-structured Interviews of clinic administrator/ manager
			Short-term facilitation*	Short-term facilitation*	Short-term facilitation*
Month 4	Survey (100% of patient study participants)	After 4th Monthly Facilitation Call	Survey of lead HIV provider	Survey of nurse/person delivering CAB + RPV LA	Survey of clinic administrator/ manager

Patient Schedule	HIV-infected participants	Staff Study Participant Schedule	Lead HIV provider	Nurse or person giving injection (Injector)	Administrators / Clinic Manager (Admin)
			Semi-structured Interview of lead HIV provider Short-term facilitation ^a	injections Semi-structured Interview of nurse/person delivering CAB + RPV LA injections Short-term facilitation*	Semi-structured Interview of clinic administrator/ manager Short-term facilitation*
Month 12/End of Study	Survey (100% of patient study participants) Semi-structured Interview (up to 4 patient study participants per site) ^b	End of Study ^c	Survey of lead HIV provider Semi-structured Interview of lead HIV provider	Survey of nurse/person delivering CAB + RPV LA injections Semi-structured Interview of nurse/person delivering CAB + RPV LA injections	Survey of clinic administrator/ manager Semi-structured Interview of clinic administrator/ manager

- a) Short-term facilitation calls with the staff study participants (Investigator, nurse and clinic manager are expected to attend each call, but at least one person from each site must be present) will occur monthly for at least 6 months. Facilitation calls will begin after sites begin enrolling patient study participants. Facilitation calls will continue during the enrollment period until the last enrolled subject achieves their Month 6 study visit.
- b) Semi-structured interviews for patient study participants should be conducted within approximately 4 weeks of their Month 12 study visit.

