Enrollment of Staff Study Participants: Investigational sites will be selected and staff study participants (lead HIV care providers (HCPs), Nurses/staff performing CAB + RPV LA injections, and administrators/clinic managers) will be identified prior to study commencement. Upon study initiation, clinical sites will have up to 2 months to engage and enrol up to 15 patient study participants into this study. Key objectives of this study relate to the delivery of the CAB + RPV LA regimen at a clinic, including the learning process clinic staff will undergo for this paradigm-changing regimen. One of the goals is to facilitate shared learnings across clinics in order to drive successful implementation, and this will be conducted through the short-term facilitation calls with study personnel. Thus, it is necessary for participating sites to initiate and complete enrolment concurrently within a short time frame. A limited enrolment period of up to 2 months is proposed with a goal to have approximately 80% of participating clinics fully prepared to enrol at the time of study commencement. Adjustments to this time frame will be considered by the sponsor study team based upon study progress and may include an extension of the enrolment period for up to a maximum of 4 months; if the enrolment period is extended beyond 2 months, enrolment caps at individual sites may be raised beyond 15, up to the study maximum of 135 patient study participants.

All lead investigators, nurses/injectors, and/or administrators responsible for implementation will attend an in-person investigator meeting prior to study start. The purpose of this meeting is to educate healthcare staff on the CAB + RPV LA regimen, including the proper administration of the regimen, protocol requirements for all study participants, data collection methods and an overview of available support tools (toolkit). Additionally, an overview of the key protocol objectives and relevant implementation science elements will be reviewed.

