Upon study initiation, investigational sites will begin enrolment of eligible patient study participants into the study. Patient study participant enrolment is expected to continue for approximately 2 months. During the period after enrolment commences, patients will be screened and sites will begin to deliver the CAB + RPV LA regimen. Continuing through the last enrolled patient study participant achieving their Month 6 visit in the study CAB + RPV LA, staff study participants will receive short-term facilitation calls in addition to the available support tools (toolkit). The core component of the facilitation includes

structured monthly group coaching calls (inclusive of all participating clinics) facilitated through the study team/ CRO partners. The purpose of the monthly group facilitation/coaching calls is to share best practices, discuss alternative work flows, discuss support tools, and help identify barriers and facilitators to the successful delivery of the CAB + RPV LA regimen. After the last enrolled patient study participant achieves the Month 6 visit, the short-term facilitation calls will be discontinued. Following an additional 6 months during which no external facilitation occurs (Month 6 to Month 12), sustainment of implementation strategies will be assessed via surveys and semi-structured interviews of staff study participants as well as patient study participants. During the course of the study, staff study participants will be asked about their utilization of each element of the toolkit. For example, if they found the injection training video useful, which tools they used, for how long, and if they used any clinic-developed implementation strategies (not part of the study “toolkit”) to facilitate successful utilization and sustainment of CAB + RPV LA. This data will be captured in the surveys and semi-structured interviews.

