- n. **Note:** Patient study participants with \geq Grade 1 LFTs at screening and or day 1 must be discussed with the Medical Monitor prior to initiation of LA dosing; continuation in the study or progression onto LA dosing may require additional evaluations, including labs drawn after a period of oral dosing with CAB + RPV.
- o. Follow Up Visit - Conduct ~4 weeks after the last dose of investigational product (IP) if not entering Long-Term Follow Up and only if the participant has ongoing AEs or lab abnormalities at the last on-study visit. May be conducted by telephone.

Table 4 Schedule of Assessments Table for Staff Study Participants

Procedures	Prior to Enrollment	Intervention Period (Month)										
		Day 1	1	2	3	4	5	6	7	8	9	12
Staff Study Participant Questionnaire		X ^a				X ^b						X ^b
Staff Study Participant Interviews (SSI)		X ^a				X ^b						X ^b
Staff Study Participant Monthly Facilitation Calls ^c		X	X	X	X	X	X	X	X	X	X	

- a. Questionnaire and interview should be conducted prior to the first patient receiving their first CAB + RPV LA injection at that site.
- b. Questionnaire and interview should be conducted within approximately 4 weeks of the targeted subject visit at each site for Month 4 and after at least 50% of patient study participant visits at Month 12.
- c. Facilitation calls will continue during the enrollment period until the last enrolled subject achieves their Month 6 study visit.

Table 5 Schedule of Activities Table for Patient Study Participants (Long Term Follow Up)^a

Procedures for Long-Term Follow Up ^a	Month 3	Month 6	Month 9	Month 12	WD	Notes

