Aim 3: To identify the optimized complex implementation strategy required for successful implementation of CAB + RPV LA in various clinical settings and contexts;

Aim 4: To measure patient satisfaction with the process (timeliness of visits, length of visit, and patient education).

Implementation Stage of Research Project:

Initial implementation stage: the first use of an evidence-based intervention (i.e., CAB + RPV LA) by healthcare professionals and patients/service users in pragmatic clinical care settings and learning how to support successful implementation into routine care.

The LATTE and LATTE-2 studies have demonstrated the efficacy of maintaining viral load suppression in participants who initiated a three drug ARV regimen prior to switching to the two-drug CAB + RPV regimen. Specifically, phase 2b studies including LATTE and LATTE-2 provided a proof of concept for a two-drug regimen in patients initially suppressed on three drugs. The LATTE study provided valuable information on both the optimal dose of oral CAB and the importance of an induction/maintenance approach to HIV therapy. The LATTE-2 study demonstrated the ability of a 2-drug maintenance therapy of LA CAB and LA RPV to maintain virologic suppression in patients who initiated on a triple antiretroviral oral based regimen

Several larger, phase 3 studies are currently underway (ATLAS, ATLAS-2M, and FLAIR) that will test the effectiveness of CAB + RPV LA in maintaining viral load suppression in patients initially suppressed on a three-drug regimen.

Design of Implementation Research:

Hybrid III: The primary focus of this study is implementation of mostly provider-focused implementation strategies (suite of training and implementation tools as well as short-term intensive facilitation); The secondary focus is on the clinical efficacy of this novel approach to antiretroviral therapy for the treatment of HIV infection (CAB + RPV LA). Implementation research outcomes are different than clinical outcomes more commonly incorporated into clinical trial research and design. In Implementation Science, research outcomes are typically provider and/or system behaviours rather than patient clinical outcomes. For example, outcomes can include levels and rates of acceptability, adoption, and fidelity to the clinical intervention [Proctor, 2011].

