8.2.2. Staff Study Participants

Surveys and Questionnaires for staff study participants should be performed/ collected prior to the first Patient Study Participant CAB + RPV LA injection, but may be conducted after Patient Study Participant screening or Day 1 visits.

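### The staff baseline for the primary AIM/IAM/FIM change score need not precede the site's first facilitation call, so exposure at baseline can differ between sites

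*Protocol*

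**What the plan says.** Section 4.1 describes a single-arm evaluation of the effect of an implementation strategy. Sections 2.2 and 4.2 define that strategy as training, implementation tools and short-term facilitation. Section 2.2 adds that "The primary focus of this study is implementation of mostly provider-focused implementation strategies", and its theory-of-change text names external facilitation as a core component. The primary staff endpoint is change from baseline to Month 12 in AIM, IAM and FIM (Sections 9.2 and 9.4.1).

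The timing of the staff baseline is set in several places:

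- Appendix 11 (Section 10.11): "following the investigator meeting, but prior to any patients at the site receiving the CAB+RPV injection".
- Section 1.5, Table 4, note a: "Questionnaire and interview should be conducted prior to the first patient receiving their first CAB + RPV LA injection at that site".
- Section 8.2.2: the survey precedes the first injection, "but may be conducted after Patient Study Participant screening or Day 1 visits".

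On the investigator meeting, Section 1.3 says: "The purpose of this meeting is to educate healthcare staff on the CAB + RPV LA regimen". The meeting also introduces the toolkit.

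On the calls, Section 1.3 (Table 1, note a) says: "Facilitation calls will begin after sites begin enrolling patient study participants". The same section describes them as monthly group calls that take in every participating clinic. Table 4 marks a call in the Day 1 column, which also holds the baseline questionnaire. Its Prior to Enrollment column is empty.

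**The concern.** With no control arm, the baseline survey is what the Month 12 staff scores are compared with. Its only deadline is the site's first injection, which comes about a month after that site's first Day 1 visit. The calls run on a different clock, starting when sites begin enrolling. Nothing links the two, so the number of coaching calls behind a site's baseline depends on when its first patient happens to enter.

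What is at stake is the meaning of the primary change score. Any shift in staff opinion produced by a call before baseline goes into the reference instead of the change, and by different amounts at different sites. An analysis plan cannot recover a pre-call measurement that was never taken, so the timing has to be settled in the protocol.

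**Working it through.** The protocol gives no count of calls before baseline, so there is no stated figure to reproduce on this point. Section 9.2 does give a precision figure for the site-level change, a half-width of 0.55 for 9 sites at SD 1. The usual formula gives 1.96 × 1/√9 = 0.65, or 1.96 × 0.50/√9 = 0.33 with the SD that the same section expects. That is a separate matter, and nothing below depends on it.

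**Inputs**

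- Calls: monthly, shared by all clinics, starting once sites enrol (Section 1.3).
- Oral lead-in before the first injection: 1 month (Section 1.3).
- Enrolment: 2 months planned, 4 months at most (Section 1.3).
- Baseline deadline: the site's first injection (Table 4, note a).

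**Assumptions**

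- There is one shared series of calls.
- The first call falls at time c after the first site enrols, with 0 ≤ c < 1 month.
- Enrolment is counted from Day 1.

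**Count.** If a site's first Day 1 is at study month E, its first injection is at E + 1. Calls fall at c, c + 1, c + 2 and so on. The number falling before E + 1 is E + 1 for whole-number E, whatever c is in that range.

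| Site's first Day 1 (month E) | First injection | Calls possible before baseline |
|---|---|---|
| 0 | 1 | 1 |
| 1 | 2 | 2 |
| 2 (end of planned enrolment) | 3 | 3 |
| 3 (extension only) | 4 | 4 |
| 4 (maximum extension) | 5 | 5 |

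If calls instead started separately at each site's own enrolment, the count would be 1, or 2 if the Month 1 call came before that day's injection.

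**How many sites.** Section 1.3 aims for about 80% of clinics ready at commencement: 0.8 × 9 = 7.2, leaving about 2 of 9 that may start later.

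**Effect on the score.** Let D be the full shift from before any call to Month 12, and f the share of D that has occurred by baseline. The measured change is (1 − f)D. The documents give neither value. With an assumed D of 0.5 points, f = 0.25, 0.50 and 0.75 give 0.375, 0.25 and 0.125. If early exposure moved scores the other way, say f = −0.25, the measured change would be 1.25 × 0.5 = 0.625. If 2 of 9 sites carry an extra pre-baseline shift, the overall mean moves by 2/9 = 0.22 of that shift. In a site type with three sites (an even split is assumed), one such site moves that type's mean by 1/3 of it.

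**The case against.** The strongest defence is that the survey items rate the injection, not the calls or the toolkit. The primary objective is worded as delivering CAB + RPV LA, and Appendix 11 asks for expectations at baseline and experience later. Staff at sites that have never delivered the regimen need some briefing before they can form an expectation, so a baseline after training is defensible. This stands. A survey before training would be a trade-off, and its absence is not an error.

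It is also fair that Section 1.3 plans concurrent start-up, that Table 4 places the questionnaire at Day 1, and that Table 1 lists the baseline survey above the first facilitation row. Three or more prior calls would need a site whose first patient enters late. That stands as a limit on size. None of these places, however, makes baseline before the first call a rule.

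Consequences are also limited. Section 9.1 plans no hypothesis test, and exploration of variability by site type and setting is labelled exploratory in Section 9.4. Patient-level AIM and IAM involve no facilitation calls.

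Two stronger readings are tempting and not supported:

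- A reader might infer that a late site's baseline could coincide with or follow the interim survey, because that survey comes after the fourth call. Table 4, note b, ties the second questionnaire to within about 4 weeks of the site's Month 4 visit. It should therefore fall no earlier than about Month 3 at that site, some two months after the baseline deadline.
- A reader might infer that the change score understates the strategy's effect. Section 2.2 reports mixed provider reactions and worries about burden, so early exposure could raise or lower expectations. The documents do not settle the direction.

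**Conclusion.** The point holds as a gap in timing. The staff reference for the primary change score is not kept ahead of the facilitation calls, and exposure can differ by site: about one call at a promptly enrolling site, and up to about three at a late one within the planned 2 months. Four or five would require both an extension and a late first patient. These counts rest on one shared monthly series that begins within a month of the first site's enrolment; site-by-site calls would give one or two.

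The score remains interpretable as change from a trained, pre-injection expectation to Month 12 experience. It does not measure the effect of the whole strategy as Section 4.1 words it, because training and the toolkit introduction precede baseline at every site by design. Since the direction is unknown and the analysis is descriptive, this is a low-cost improvement and not a flaw that invalidates the endpoint.

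**What to change.** Require each site's staff baseline survey and interview to be completed before that site's first facilitation call, for example by moving the mark in Table 4 to its Prior to Enrollment column. Align the timing wording in Section 1.2, Section 1.3 (Table 1 and the key informant interview text), Table 4 note a, Section 3, Section 8.2.2 and Appendix 11.

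For sites already started, record how many calls staff attended before baseline, and show the primary change with and without sites whose baseline followed a call. With about 9 sites the reduced set may be small, so list the call counts by site as well.

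Describe the endpoint as change after initial training. No survey before training is needed for this fix.

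The cost is protocol wording and an earlier survey date. Staff are already identified before study commencement, so no new visit or personnel is involved.

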10.12. Appendix 12: COVID-19 Pandemic and Clinical Trial Continuity

Background

The COVID-19 pandemic presents significant logistical challenges for many clinical sites around the world, with variable restrictions being placed on site resources and operations, and on an individual participants ability to attend clinic visits. In some places, medical visits are occurring, and in others, research clinics are operating with only emergency staff.

Based on these challenges, it may be necessary to adopt additional measures and procedures to protect participant safety, and to ensure that there are no gaps in HIV-1 treatment for participants enrolled in this clinical study, through continuous access to antiretroviral therapy.

In order to maintain the scientific integrity of the study, and adhere to updated guidance from regulators, procedures have also been put into place to ensure that the actions taken to mitigate against any impact of COVID-19 are well documented in the trial database.

A “Memo to Investigators” was issued on March 18th, 2020 and served as a record of approved emergency actions being taken within this clinical trial to manage issues related to COVID-19. That memo continues to serve as record of approved actions which can be fully implemented by Investigators, in advance of this protocol guidance. This appendix will remain consistent with the guidance provided within the “Memo to Investigators” and will also serve to provide additional protocol documentation requirements and procedures.

This appendix outlines the measures which are approved for implementation within this clinical trial, to protect patient safety and to ensure the integrity of the clinical trial, as a result of COVID-19 only. These measures may be implemented in accordance with any requirements and expectations set out by local Independent Review Boards/Independent Ethics Committees and National Competent Authorities, as necessary.

This appendix **does not** apply to participant management issues that are unrelated to a specific, and documented, impact from COVID-19.

10.12.1. Changes to Study Visits and Study Procedures

- Where site staff resource is constrained due to COVID-19, IM dosing visits may proceed with limited or no other protocol-defined assessments (e.g. lab tests, questionnaires, etc.). If lab tests will be missed for more than one consecutive visit, the medical monitor must be contacted, to provide guidance for safety monitoring.
- For FRP, point of care pregnancy testing should be performed, prior to IM dosing.
- If central laboratory testing cannot be performed at a particular visit, and monitoring for safety is required, tests may be performed at an appropriately authorised/accredited local laboratory (or other relevant clinical facility), if this

can be done within local restrictions on physical distancing. The site should proactively inform the sponsor about such instances. Local laboratory results may be used to inform safety decisions. Results should be retained in source records.

- When on-site visits are reduced, it is important that the investigator continue collecting relevant clinical information, including adverse events, from the participant through alternative means, e.g. by telephone contact.
- There may be cases where the current principal investigator (PI) of a site is indisposed for a period and may need to delegate parts of his/her duties temporarily, e.g. to a sub-investigator. Any such changes should be documented in the site's source records. Any permanent changes in PI should be communicated to the sponsor.
- There may also be circumstances where immediate actions are required by the sponsor and/or investigator, outside of what is contemplated in the protocol, in order to protect a study participant from immediate hazard. Any such measures will be carefully documented and conducted in accordance with the National Competent Authority (NCA)/IRB/IEC regulations.

